7 STUDY PROCEDURES AND DATA COLLECTION

7.1 VISIT SCHEDULE

Table 2 - Timing of cohort enrollment, interviews, examinations, medical records

	<20 weeks' gestation	16-20 weeks' gestation	26-32 weeks' gestation	0-6 weeks after delivery	0-6 months after delivery	1 year after delivery
Referral	X					
Enrollment and Consent	X					
Intake Interview	X					
Interim Interview I		X				
Interim Interview II			X			
Outcome Interview				X		
Medical Record Review					X	
Dysmorphological Examination						X
Pediatric Medical Record Review and Questionnaire at 1 Year						X

*outcome interview and medical record review will be performed within 6 weeks and 6 months respectively following the end of pregnancies that result in spontaneous abortion, elective termination or stillbirth.

7.2 DATA COLLECTED FROM THE MOTHER

Following oral administration of informed consent, a structured maternal intake telephone interview will be conducted by a trained Research Associate at OTIS. This interview will include questions as itemized below and information will be updated at all subsequent maternal interviews. Women who have had teriflunomide exposure will be informed that teriflunomide serum levels and elimination procedures can be arranged through their health care provider and/or the teriflunomide patient management program.

Following the initial intake interview, participants will be sent a pregnancy diary on which they will be asked to record any additional exposures or events as the pregnancy progresses. Women who have enrolled in the study prior to 16 weeks post-LMP will be interviewed by telephone at 20-22 weeks post-LMP, 32-34 weeks post-LMP and within 6 weeks after the expected due date. Women who have enrolled between 16 and 20 weeks post-LMP will be interviewed at 32-34 weeks post-LMP and within 6 weeks after expected due date (see

OSD-003149 VERSION N°1.0 (20-JUL-2010)

Ensure that the printed copy of this document is the current version available on the Intranet.

Table 2). The purpose of these interviews will be to update records of pregnancy exposures and results of prenatal tests, to remind women to maintain the exposure diary, to update phone number and address information, and to determine if the pregnancy has ended prior to the expected due date. The maternal outcome interview will be conducted within approximately 4 weeks of the end of the pregnancy.

Data collected from these interviews and the diary includes the following:

During Pregnancy:

- History of previous pregnancy outcomes
- Health and family medical history including history of MS disease
- Socioeconomic and demographic information including occupation, education, race/ethnicity of mother and father, and family income category
- Course of current pregnancy including prenatal tests, test results, pre-pregnancy body mass index
- Exposures during the current pregnancy including over-the-counter and prescription medications including all treatments for MS, vitamin supplements, herbal products, tobacco, alcohol, illicit drugs, occupational and environmental exposures
- Dosage and dates of teriflunomide
- Cholestyramine or charcoal elimination procedure(s), dates and compliance
- If blood levels for teriflunomide were measured, dates and results
- Measure of MS disease severity/activity

At Completion of Pregnancy:

- The outcome of pregnancy
- Gestational age at pregnancy end
- Sex of the infant (s)
- Delivery type
- Type of hospital stay
- Maternal and infant complications
- Maternal weight gain
- Major structural defects,
- Birth weight, length, head circumference
- Apgar scores
- Method of infant feeding

- Additional medications or tests since last interview

7.2.1 Site / Investigator questionnaires

Not Applicable.

7.2.2 Screening log

The study center maintains a record of eligible and ineligible pregnancies for the cohort study, as well as a record of eligible pregnant women who decline or consent to enrollment.

7.2.3 Data Collected from medical records

Medical records from the prenatal care provider, the hospital of delivery, the neurologist, the pediatrician, and any other specialty provider such as a pathologist, if relevant, will be examined for additional exposure and outcome data. Upon completion of the outcome interview, regardless of the outcome of the pregnancy, each woman will be mailed a packet containing medical records release forms for the delivery hospital, obstetrician, pediatrician, and neurologist if applicable, as well as the laboratory results, if blood levels of teriflunomide were obtained at any time point during or just prior to pregnancy and documentation of courses and dates of the drug elimination procedure. Each woman will be asked to sign the medical records release forms and to return them along with the pregnancy exposure diary form.

Upon receipt of the signed medical records release forms, a standard physical evaluation form will be mailed to the physician responsible for the care of each live born infant at or near 1 year of age. This form includes information on infant size at the time of the latest examination and an open-ended question about postnatal complications and congenital anomalies.

Data abstracted from the medical records include the following:

- Prenatal tests and results
- Measures of disease activity/severity during pregnancy, age at diagnosis
- Blood levels of teriflunomide and dates measured (if available)
- Courses of cholestyramine or charcoal prescribed and dates
- Outcome of pregnancy
- Gestational age at pregnancy end
- Sex of the infant (s)
- Delivery type
- Type of hospital stay
- Maternal and infant complications

- Maternal weight gain, pre-pregnancy body mass index
- Major structural defects, and any diagnostic tests to confirm
- Birth weight, length, head circumference
- Postnatal weight, length, head circumference
- Apgar scores
- Method of infant feeding
- Pathology results, if relevant, e.g., for stillbirths

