6.2.1 Inclusion criteria for the cohort study

Cohort I: Teriflunomide-exposed pregnant women with MS

- Pregnant women who have previously been treated with teriflunomide, including women who were treated during a clinical trial, who are participating in another registry, or who are treated with other approved disease modifying therapy for MS, for any number of days, at any dose, and at anytime from the 1st day of the last menstrual period up to and including the 12th week after the first day of the LMP.
- Pregnant women who have provided an oral and/or written consent to enroll no later than 20 completed weeks from LMP.
- Pregnant women who agree to the conditions and requirements of the study including the interview schedule, release of medical records, and the physical examination of live born infants (up to 1 year post birth).

Cohort II – Pregnant women with MS not exposed to teriflunomide during the current pregnancy

- Pregnant women with a diagnosis of MS who have:
 1. Not taken teriflunomide at any time but who may or may not have taken another medication for MS during the current pregnancy, **or**
 2. Previously been treated with teriflunomide within 2 years prior to the index pregnancy and have documented blood levels below 0.02 mcg/mL prior to pregnancy, **or**
 3. Previously been treated with teriflunomide greater than 2 years prior to the index pregnancy
- Pregnant women who have provided oral and/or written consent to enroll no later than 20 completed weeks from LMP.
- Pregnant women who agree to the conditions and requirements of the study including the interview schedule, release of medical records, and the physical examination of live born infants (up to 1 year post birth)
- Pregnant women can be taking any other approved disease modifying therapy for MS

Cohort III - Pregnant women without MS and no exposure to any known human teratogen

- Pregnant women who do not have a known diagnosis of MS and have no known exposure to a known human teratogen, as determined by the referring Teratogen Information Specialists and confirmed by the OTIS Research Center.
- Pregnant women who have provided oral and/or written consent to enroll no later than 20 completed weeks from LMP.
- Pregnant women who agree to the conditions and requirements of the study including the interview schedule, release of medical records, and the physical examination of live born infants (up to 1 year post birth).

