7.2.3.4 Outcome classification for secondary endpoints for cohort study

- Pattern of minor structural defects is defined as any 2 or more infants receiving the study dysmorphology examination in the teriflunomide-exposed cohort (Cohort I) who have the same 3 or more minor structural defects. If a pattern or patterns are identified, the prevalence of the same pattern in Cohorts II and III is evaluated.
- Spontaneous abortion: spontaneous abortion is defined as non-deliberate fetal death which occurs prior to 20 completed week's post-LMP.
- Elective abortion: elective abortion is defined as deliberate termination of pregnancy at any time in gestation.
- Stillbirth: stillbirth is defined as non-deliberate fetal death anytime in gestation at or after 20 completed week's post-LMP.
- Premature delivery: premature delivery is defined as live birth prior to 37 completed weeks gestation as counted from LMP (or calculated from first-trimester ultrasound-derived due date if last menstrual period uncertain or more than 1 week discrepant).

CSD-003149 VERSION N°1.0 (20-JUL-2010)

Ensure that the printed copy of this document is the current version available on the Intranet.

Elective cesarean deliveries or inductions prior to 37 completed weeks will be considered separately.

- Small for gestational age: small for gestational age is defined as birth size (weight, length or head circumference) less than or equal to the 10th percentile for sex and gestational age using National Center for Health Statistic (NCHS) pediatric growth curves for full term infants. Prenatal growth curves will be used for premature infants.
- Postnatal growth deficiency up to 1 year of age: postnatal growth deficiency is defined as postnatal size (weight, length or head circumference) less than or equal to the 10th percentile for sex and age using NCHS pediatric growth curves, and adjusted postnatal age for premature infants.
- Lost-to-follow-up: Subjects will be considered lost-to-follow-up if they have completed the initial intake interview but subsequently fail to complete the outcome interview and medical records release despite a standard number of telephone attempts and attempt to contact by mail as per study procedure manual within 1 year of the mother's estimated due date. Voluntary subject withdrawals will be considered separately.

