8.1 ANALYSIS POPULATION

This study consists of 3 cohorts recruited from the United States and Canada. The exposed group (Cohort I) consists of pregnant women with a confirmed diagnosis of MS and

teriflunomide exposure at anytime from the 1st day of LMP up to and including the 12th week after the first day of the LMP. The diseased comparison group (Cohort II) consists of pregnant women with a confirmed diagnosis of MS who have not been exposed to teriflunomide during the current pregnancy. The healthy comparison group (Cohort III) consists of pregnant women who do not have MS and have no known exposure to any known teratogen or teriflunomide. Participants who are deemed lost-to-follow-up or who withdraw before the known outcome of pregnancy (Section 7.3) will be reported in descriptive tables in all interim and final reports, but will be excluded from statistical comparisons.

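### Record releases are mailed only after the outcome interview, so records cannot recover the outcome of a woman who misses it, and Sections 7.2.3.4 and 7.3 define loss to follow-up differently

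*Protocol*

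**What the plan says.** Protocol Section 7.2.3 lists records from the prenatal provider, delivery hospital, neurologist and pediatrician as sources of further exposure and outcome data. The releases for them have one trigger: "Upon completion of the outcome interview, regardless of the outcome of the pregnancy, each woman will be mailed a packet" holding the release forms and the request for any teriflunomide laboratory results. The 1-year form for the infant's physician is mailed only once signed releases have come back.

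The interview itself follows the end of pregnancy. Section 7.2 says: "The maternal outcome interview will be conducted within approximately 4 weeks of the end of the pregnancy". The footnote to Table 2 (Section 7.1) says that "outcome interview and medical record review will be performed within 6 weeks and 6 months respectively following the end of pregnancies" ending in a loss or termination. For deliveries, Table 2 places record review at 0-6 months.

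Two sections define loss to follow-up. Section 7.2.3.4 covers women who finish intake but "subsequently fail to complete the outcome interview and medical records release" despite telephone and mail attempts up to one year past the due date. Section 7.3 counts a woman as lost if she does not complete the outcome interview, and does not mention the release. Section 8.1, citing Section 7.3, reports lost women descriptively and leaves them out of the statistical comparisons.

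**The concern.** Section 5.4 names four sources for the primary outcome: maternal report, record review, the 1-year pediatric evaluation and the dysmorphology examination. Two of these, record review and the pediatric form, depend on a single mailing that goes out after the pregnancy has ended, and only to women who have already given the outcome interview. Records would be most useful for a woman who cannot be reached by telephone, yet she is the one for whom the plan never requests them.

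Her pregnancy then drops out of the comparison. If missing the interview is related to outcome, that exclusion is informative. The documents give no figure on whether it is. An SAP cannot repair this afterwards, because records that were never requested cannot be analyzed.

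**Working it through.** **Step 1. Follow one woman through the rules.** She enrolls, completes intake and misses the outcome interview.

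| Protocol section | Rule | Consequence for her |
|---|---|---|
| 7.2.3 | Packet sent once the interview is complete | No release forms are sent |
| 7.2.3 | Pediatric form sent on receipt of signed releases | No 1-year form is sent |
| 7.3 | No outcome interview means lost | Classed as lost |
| 8.1 | Lost women left out of comparisons | Not analyzed |

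No other trigger for the releases is described, so her records cannot change the result at any point in this chain.

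**Step 2. Compare the two definitions.** Section 7.2.3.4 can be read in two ways.

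- *Lost means failing both items.* Under the Section 7.2.3 sequence, missing the interview always means having no release, so the release condition adds nothing. If a release could be obtained separately, a woman with a release but no interview would be lost under 7.3 and not lost under 7.2.3.4.
- *Lost means not completing the pair.* A woman who gives the interview but does not return the release would be lost under 7.2.3.4 and not lost under 7.3.

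On either reading Sections 7.2.3, 7.2.3.4 and 7.3 have to be reconciled.

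**Step 3. Size.** Inputs from Section 8.4: 75 exposed and 125 per comparison group enrolled, 4% loss, 64 and 106 live births, 3% baseline rate, detectable relative risk 5.57.

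The plan's own figures come first. The 85% yield reproduces: 0.85 x 75 = 63.75 and 0.85 x 125 = 106.25. The detectable risk also reproduces. At 64:106, with 0.03 x 5.57 = 16.7% against 3%, exact enumeration of the two-sided Fisher test (twice the smaller tail) gives 80.9% power. The sample size already allows for the 4% loss and is not in dispute here.

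Women lost at the stated rate:
- exposed: 0.04 x 75 = 3
- each comparison group: 0.04 x 125 = 5

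Expected major defects among them, counting every lost pregnancy as a live birth (a generous assumption):
- exposed, at 3%: 3 x 0.03 = 0.09
- each comparison group, at 3%: 5 x 0.03 = 0.15
- exposed, if the risk were the detectable 16.7%: 3 x 0.167 = 0.50

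The share that records would recover is not given. The gain therefore lies between nothing and these values.

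For context, the expected count in the exposed live births is 64 x 0.03 = 1.92, and one case is 1/64 = 1.6 percentage points. That is how sensitive the rate is to any single case. It does not measure this defect.

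**The case against.** The case on the other side has several parts.

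- *The post-delivery packet is a reasonable choice.* Delivery type, birth size, Apgar scores, pathology and postnatal growth do not exist until after birth, and early releases may lapse. This stands as a reason to keep a postnatal step. It does not explain why no release is taken earlier.
- *Other contacts exist.* Agreeing to record release is an inclusion criterion (6.2.1). Signed study and HIPAA consent may come by mail or at the infant examination (6.3.2). Interim interviews ask whether the pregnancy has ended (7.2), and contact attempts run to one year past the due date (7.3). A procedure manual not available here may say more. All of this makes loss less likely. But agreeing in principle is not a signed provider release, and none of these sections opens a records route for a woman who misses the interview, whom Section 7.3 still classes as lost.
- *The numbers are small.* This stands in full. The 4% covers all loss, and only part of it would be recovered.

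A reader might infer something stronger: that cohort membership itself is settled after the outcome is known. The analysis population requires "pregnant women with a confirmed diagnosis of MS who have not been exposed to teriflunomide during the current pregnancy", and recently treated women enter Cohort II only if they "have documented blood levels below 0.02 mcg/mL prior to pregnancy"; the packet is the only documentary route described for either fact. The protocol does not support that inference. Section 6.3.2 has criteria screened and verified by Research Center staff at enrollment. Section 6.2.2 makes the documented level an entry condition, and Section 7.2 asks about MS history and blood levels from intake. Section 7.2.3 does not describe record abstraction as an eligibility check, and no section removes or reassigns a woman on a late record. What remains is narrower: the protocol names no source document for these two facts at enrollment.

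**Conclusion.** The point holds as a data-collection weakness together with a conflict between definitions. As written, a missed outcome interview closes the records route and leads to exclusion from the comparisons, and the two lost-to-follow-up definitions do not agree.

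The size is modest: about 3 exposed women and 5 in each comparison group, carrying roughly 0.1 to 0.15 expected defects per group at 3%, or about 0.5 in the exposed if their risk were at the detectable level. These figures assume that the 4% loss is realized, that it applies equally to each cohort, and that every lost pregnancy would have been a live birth. If loss were higher or related to outcome, the effect would be larger, but the documents give no basis for a figure. The number of women entering Cohort II by the blood-level route is not stated, so nothing can be computed for that part, and no claim is made that eligibility is decided or revised after the outcome. The change is worth making because it is cheap and the study expects few events.

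**What to change.** 1. In Section 7.2.3, mail the release forms for providers already known (obstetrician, neurologist, teriflunomide laboratory result, planned delivery hospital) with the pregnancy diary that Section 7.2 already sends after intake. Collect or update the delivery hospital and pediatrician releases at the outcome interview.
2. Use the early releases to obtain the pregnancy outcome for women who miss the interview. Withdrawals remain a separate category, as now.
3. Put one definition in Sections 7.2.3.4 and 7.3: a woman is lost only if neither interview nor records yield the outcome. Let Section 8.1 refer to it.
4. As a by-product, name the source document for MS diagnosis and for the pre-pregnancy blood level. With early releases, that evidence can be obtained before the outcome.

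The cost is protocol wording, a procedure update and an earlier mailing. The drawback is that some releases may expire or need re-signing after delivery, for instance when the delivery hospital differs from the one planned.

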Ensure that the printed copy of this document is the current version available on the Intranet.

OSD-003149 VERSION N°1.0 (20-JUL-2010)

	
 • pre-pregnancy maternal body mass index • course of current pregnancy including prenatal tests • exposure type, dates and dosages during the current pregnancy including all MS medications, other medications including over-the-counter and prescription products, vitamin and mineral supplements, vaccines, illness, fever, procedures • blood levels of teriflunomide and dates, courses of drug elimination procedures and dates • measures of disease activity/severity during pregnancy, age at diagnosis 
Pregnancy and Birth Outcomes:
 
 • the outcome of pregnancy • gestational age, sex of infant(s), delivery type, including cesarean section, length and type of hospital stay, maternal and infant complications • maternal weight gain • Apgar scores • major structural defects • birth weight, length and head circumference • method of infant feeding • pathology results, if relevant 
Postnatal Outcomes for Live Born Infants:
 
 • Physical examination by one of a team of study pediatricians who are dysmorphologists/geneticists for both major and minor structural anomalies in first year of life, as well as growth • Growth and development within 6 months of delivery and at 1 year of age evaluated by general pediatrician

Statistical methodology
	
 • The primary analysis variable is rate of major structural defects in live born infants in the first year of life. • The group comparisons will be carried out using Fisher’s exact test. Multivariate analysis, adjusting for confounders, will be conducted where feasible. • The secondary analysis variables include proportion of major

Ensure that the printed copy of this document is the current version available on the Intranet.

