8.3 STATISTICAL METHODS

8.3.1 Primary endpoint

The primary endpoint is rate of major structural defects in live born infants. Due to the expected low incidences of major defects, diagnosed within the first year of life, the primary comparison will be carried out using Fisher's exact test between the teriflunomide-exposed group (Cohort I) and the disease-matched comparison group (Cohort II). Although Cohort II is "matched" to Cohort I on the underlying maternal diagnosis of MS, no a priori matching on disease severity is performed at the time of recruitment. Therefore, measures of MS severity will be addressed as confounders in the analyses comparing Cohort I to Cohort II as described below.

Due to the observational nature of the study, it is necessary to adjust for confounders to address baseline differences between the teriflunomide exposed and the comparison groups.

Ensure that the printed copy of this document is the current version available on the Intranet.

The potential confounders to be evaluated will be those itemized in the analysis variables in [Section 8.2](#) (e.g., maternal age, MS severity). Confounders will be those variables that modify the odds ratio for the outcome by at least 10% in logistic regression with exposure to teriflunomide and the potential confounder as predictors. In addition, any variable that is deemed to be clinically relevant will be considered for inclusion in multivariate analysis even if the 10% criterion is not met. The adjustment for confounders will be carried out using logistic regression, the primary outcome variable as the dependent variable, and with confounders included in the models as independent variables adjusting for the effect of exposure. Stepwise procedures will be used in case of many identified confounders, as sample size permits. Propensity scoring methods will be considered. The analysis of major birth defects will be further stratified based on prenatal diagnosis performed prior to enrollment or not.

Secondary comparisons will be made between the teriflunomide exposed group (Cohort I) and the healthy comparison group (Cohort III). The rate of major structural defects will also be compared to the most recently available rate from the MACDP.

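### The plan relies on adjusting for MS severity, but the only severity data it dates come from pregnancy, at or after exposure, and no rule limits the adjuster to pre-exposure values

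*Protocol*

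**What the plan says.** - **Need for adjustment.** Section 8.3.1 states that "no a priori matching on disease severity is performed at the time of recruitment". It concludes that "measures of MS severity will be addressed as confounders in the analyses comparing Cohort I to Cohort II". The same section gives the purpose of adjustment as dealing with baseline differences between the groups.
- **Candidate list.** Section 8.2 names disease severity among variables that may or may not enter as confounders. It gives no time point.
- **Selection rule.** In 8.3.1, "Confounders will be those variables that modify the odds ratio for the outcome by at least 10% in logistic regression". A variable judged clinically relevant may also be considered below that threshold. Neither route has a condition on timing.
- **What is collected.** From medical records, section 7.2.3 abstracts "Measures of disease activity/severity during pregnancy, age at diagnosis". The synopsis repeats the item. The maternal interview in 7.2 has a severity/activity item with no reference period, and also takes "Health and family medical history including history of MS disease", whose content is not specified. Interview items are updated at later interviews.
- **Timing.** Exposure in Cohort I is from LMP through week 12 (8.1). Enrolment is expected at 6–9 weeks post-LMP on average (8.4).
- **Where adjustment is used.** It enters logistic regression for the binary endpoints, and Cox models for spontaneous abortion and preterm delivery (8.3.2).

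**The concern.** A confounder has to be fixed before the exposure, or at least not be changed by it. Here the severity data with a stated date belong to the period during or after exposure. Activity in that period can respond to exposure status. The protocol expects nearly all exposures to occur in unintended pregnancies (3.2.1), plans to analyse drug elimination (8.3.2), and allows Cohort II women to be on other MS therapies (6.2.1). A woman's later disease activity may therefore reflect having taken, stopped or eliminated the drug.

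Two things are at stake. If the in-pregnancy value is used, the adjusted estimate may lose a part of the effect that runs through activity, or pick up bias from unmeasured causes shared by activity and outcome. And the quantity that 8.3.1 sets out to control, the difference in severity between the cohorts at baseline, may stay uncontrolled because no measurement of it has been fixed.

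**Working it through.** The plan gives no figure on this point to reproduce, so the main check is of the text.

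**1. Timing.** The exposure window opens at LMP and closes at week 12. Average intake, at 6–9 weeks, lies inside it. Anything recorded as pregnancy activity or severity is therefore concurrent with exposure or later. Section 7.2.3 does anchor other items before pregnancy: body mass index is pre-pregnancy, and blood levels are requested if taken during or just before pregnancy. Severity has no such anchor.

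**2. Would the 10% rule screen out a post-exposure variable?** This is a large-sample illustration, not an estimate for this study. From the protocol: 64 of 170 live births exposed, and a 3% defect rate, used here as the risk in unexposed women with low activity. Assumed: 30% of unexposed women have high activity, the direct exposure odds ratio (OR) is 1.5, and the ORs linking exposure to activity and activity to defects vary.

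Worked case, both link ORs equal to 2:
- High activity in the exposed: odds 2 × 0.30/0.70 = 0.857, so 46.2%.
- Unexposed risk: 0.70 × 0.0300 + 0.30 × 0.0583 = 0.0385.
- Exposed risk: 0.538 × 0.0443 + 0.462 × 0.0849 = 0.0631.
- Total OR: (0.0631/0.9369) / (0.0385/0.9615) = 1.68. The OR adjusted for activity is 1.50. Change: 1.50/1.682 − 1 = −10.8%.

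| Exposure–activity OR | Activity–defect OR | Total OR | Adjusted OR | Change |
|---|---|---|---|---|
| 0.33 | 2 | 1.298 | 1.50 | +15.6% |
| 0.33 | 3 | 1.171 | 1.50 | +28.1% |
| 0.5 | 2 | 1.357 | 1.50 | +10.6% |
| 0.5 | 3 | 1.265 | 1.50 | +18.6% |
| 2 | 2 | 1.682 | 1.50 | −10.8% |
| 2 | 3 | 1.791 | 1.50 | −16.2% |
| 3 | 2 | 1.799 | 1.50 | −16.6% |
| 3 | 3 | 1.983 | 1.50 | −24.3% |
| any of these | 1 | 1.50 | 1.50 | 0% |

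In all eight rows with both links present, the shift exceeds 10%, so the rule would keep a mediator as if it were a confounder. Two of these rows only just pass, so weaker links would fall below the threshold.

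**3. Bias from an unmeasured common cause.** Assume no drug effect, no effect of activity on defects, and an unmeasured factor raising both with ORs of 2 to 5. With exposure–activity ORs of 0.33 or 3, adjusting for activity turns a true OR of 1.00 into values from 0.89 to 1.13.

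**4. Time-to-event endpoints.** A spontaneous abortion occurs before 20 completed weeks (7.2.3.4), so fewer than 20 weeks are available for recording activity. A term pregnancy offers at least 37. The window in a loss is thus under 20/37 = 54% of that in a term birth. If activity over pregnancy enters a Cox model as a fixed covariate, its value depends partly on the outcome time.

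**The case against.** **The collected data are broader than in-pregnancy activity.** A reader might infer that nothing else is collected. The documents do not support that. The dated item is activity/severity, age at diagnosis is abstracted, MS history is taken at interview, and neurologist records are requested. The interview list headed as during pregnancy also contains past pregnancy outcomes and pre-pregnancy body mass index, so the heading dates the interview and not each variable. This objection stands in full.

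**The protocol does not say which value enters the model.** A statistical analysis plan, not shown here, could define it. That stands for the modelling choice. It does not cover the abstraction list, which is fixed in the protocol: an analysis plan can only choose among variables that have been abstracted.

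**Accounting for disease is a stated aim (3.1, 5.1).** A reader might infer that any removal of an activity-mediated component is an error. That goes too far, since a direct drug effect is a legitimate target. But 8.3.1 justifies the adjustment by baseline differences, and a direct-effect analysis would still need pre-exposure severity and would still face the bias in step 3.

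**The harm is not demonstrated.** Section 3.1 says the disease is not known to be a risk, though not comprehensively studied. Section 8.4 sees no evidence of more major defects in women with MS. With no activity–defect link, the mediator shift is zero. This stands, and it means no size can be claimed.

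**The primary test is untouched.** The primary comparison is an unadjusted Fisher's exact test, and the synopsis promises multivariate analysis only where feasible. At 3%, about 0.03 × 64 = 1.9 and 0.03 × 106 = 3.2 events are expected, and the stated detectable relative risk is 5.57. Shifts of the size shown would be small beside that. This also stands.

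**Conclusion.** The point holds in a limited form. The plan makes severity adjustment its answer to unmatched severity, dates its severity abstraction to pregnancy, and has no rule that keeps post-exposure values out of the adjustment set. As written, it can admit a consequence of exposure as a confounder, and it does not secure a pre-exposure measure.

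The consequence is confined to the adjusted logistic and Cox estimates. Its size and direction are unknown. The 11% to 28% shifts and the 0.89 to 1.13 range rest on assumed associations for which the protocol gives no values. The documents do not show that the in-pregnancy value will be the adjuster, nor that a real drug effect will be removed. This is a worthwhile improvement to the plan, not a threat to its primary conclusion.

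**What to change.** - **Section 7.2.3:** add MS severity dated before LMP to the abstraction list, for example relapses in the year before LMP, the last disability measure before LMP, and years since diagnosis. Take it from the neurologist records already requested, supplemented by the intake MS history.
- **Sections 8.2 and 8.3.1:** define the severity confounder as that pre-LMP value, for both the logistic and the Cox models.
- **In-pregnancy activity:** report it by cohort descriptively, or use it only in a labelled sensitivity analysis.

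The cost is one added abstraction item and one definition. The drawback is that some women will have no usable pre-LMP value in their records.
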